## B.12. Abbreviations and Definitions

### B.12.1. Abbreviations

Abbreviations are shown in **Table 7**.

**Table 7: Abbreviations**

Abbreviation/Acronym	Term
ADE	Adverse Device Effect
AE	Adverse Event
BSC	Boston Scientific Corporation
BTS	Bridge to Surgery
CBD	Common Bile Duct
CI	Confidence Interval
CRF	Case Report Form
CRO	Clinical Research Organization
CT	Computed Tomography
DFU	Directions for Use
eCRF	Electronic Case Report Form

**Table 7: Abbreviations**

EDC	Electronic Data Capture
ERCP	Endoscopic retrograde cholangiopancreatography
EC	Ethics Committee
FDA	Food and Drug Administration
GCP	Good Clinical Practices
ICF	Informed Consent Form
ICH	International Conference on Harmonization
ICMJE	International Committee of Medical Journal Editors
IDE	Investigational Device Exemption
IDR	Independent Data Review Board
IRB	Institutional Review Board
ISO	International Organization for Standardization
IVRS	Interactive Voice Response System
LFT	Liver Function Tests
MEDDEV	Medical Devices Directives
MRI	Magnetic Resonance Imaging
OUS	Outside of the United States
PAL	Palliative
PD	Pancreaticoduodenectomy
SADE	Serious Adverse Device Effect
SAE	Serious Adverse Event
SEMS	Self-Expanding Metal Stent
SUB-I	Sub-Investigator
UADE	Unanticipated Adverse Device Effect
USA	United States of America

1 PROTOCOL SUMMARY

Full Title	Randomized Controlled Trial Comparing Covered and Uncovered Biliary Self Expanding Metal Stents (SEMS) for Pre-operative Drainage During Neoadjuvant Therapy in Patients with Pancreatic Cancer
Abbreviated Title	Pre-operative Biliary SEMS RCT During Neoadjuvant Therapy
Primary Objective	To demonstrate non-inferiority of Fully Covered biliary SEMS to Uncovered biliary SEMS in biliary drainage for the pre-operative management of biliary obstructive symptoms caused by pancreatic cancer in patients undergoing neoadjuvant therapy.
Devices	
Stent Type:
 
FC Arm: WallFlex Biliary RX Fully Covered Stent
 
UC Arm: WallFlex Biliary RX Uncovered Stent
 
Stent Diameter:
 
8mm or 10mm
 
Stent Length:
 
40mm, 60mm, or 80mm
 
The stent length will be selected to be such that the stent length should be long enough to cover the stricture completely but to leave sufficient length of normal bile duct for subsequent anastomosis.

Device Indication	
The WallFlex Biliary RX Fully Covered Stent is indicated for use in the palliative treatment of biliary strictures produced by malignant neoplasms, relief of malignant biliary obstruction prior to surgery, and for treatment of benign biliary strictures.
 
The WallFlex Biliary RX Uncovered Stent is indicated for use in the palliative treatment of biliary strictures produced by malignant neoplasms and relief of malignant biliary obstruction prior to surgery.

Study Design	Prospective, multi-center, randomized, post-market
Primary Endpoint	
Successful pre-operative biliary drainage defined as absence of reinterventions for the management of biliary obstructive symptoms.
 
 • For patients undergoing surgery: from stent placement until surgery • For patients transitioning to palliative management: from stent placement until transition to palliation
Secondary Endpoints	
 1. Occurrence and severity of adverse events related to the stent and/or stenting procedure 2. Occurrence and severity of surgical complications 3. Occurrence and severity of peri-surgical complications (up to 30 days after surgery) 4. Ability to deploy the stent in a satisfactory position across the stricture (Stent Placement Success) 5. Improvement of biliary obstructive symptoms during stent indwell at Week 1 and Monthly until surgery or transition to palliation as applicable, compared to Baseline 6. Improvement of Laboratory Liver Function Tests (LFTs) until surgery for patients undergoing surgery, and at Week 1 and Monthly until transition to palliation, and at 1 year after stent placement for patients not undergoing surgery. 7. Biliary Reintervention rate 8. Ability to complete neoadjuvant therapy as intended without stent related interruptions of neoadjuvant therapy 9. Stent migration rate 10. Assessment by surgeon of interference, if any, of SEMS on time to surgery and/or success of pancreaticoduodenectomy 11. For patients transitioning to palliative management: Successful biliary drainage defined as absence of reinterventions for the management of biliary obstructive symptoms from stent placement to 1 year after stent placement

	
Statistical testing will be performed to determine if the rate of success when using the Fully Covered SEMS is non-inferior to the rate of success when using the Uncovered SEMS. The following hypothesis will be tested:
 $H_0: \pi_{UC} - \pi_{FC} \geq \Delta \text{ (Inferior)}$ $H_a: \pi_{UC} - \pi_{FC} < \Delta \text{ (Non-inferior)}$ 
where π_{FC} and π_{UC} are the probabilities of having success in the WallFlex Fully Covered Stent and WallFlex Uncovered Stent arms respectively, and Δ is defined as the non-inferiority margin.
 
The sample size was calculated for the test using an exact non-inferiority test. The assumed success rates for both study arms and the non-inferiority margin are guided by the following analysis of literature:
 
Hypothesis
 
The success rate estimate is extracted from a full literature search which yielded nine articles (377 patients) ^{2, 7, 21, 24, 25, 27, 29-31} on the use of metal stents for pre-operative biliary drainage. The nine articles yielded a success rate estimate of 84.6% with a 95% CI of (80.5% - 87.9%).
 
Each arm is assumed to have a success rate of 80.5%. The non-inferiority margin (Δ) is set at 20%. Given these assumptions a sample size of $51 \times 2 = 102$ patients provide 80% power to reject the null hypothesis. If the p-value calculated for the test is below 0.05 it will be concluded that the test is significant, and that the WallFlex Fully Covered stent is non-inferior to the WallFlex Uncovered stent.
 
An additional 20% of patients will be enrolled to compensate for possible loss of patients to follow-up, giving a total sample size of 122 patients.

Planned Number of Patients	122

Planned Number of Sites	6-12
Key Inclusion Criteria	
 1. Age 18 or older 2. Patient indicated for biliary metal stent placement for the treatment of jaundice and/or cholestasis 3. Willing and able to comply with the study procedures and provide written informed consent to participate in the study 4. Suspicion of pancreatic adenocarcinoma 5. Likely indicated for neoadjuvant treatment 6. Distal biliary obstruction consistent with pancreatic cancer 7. Location of distal biliary obstruction such that it would allow the proximal end of a stent to be positioned at least 2 cm from the hilum 8. Endoscopic and surgical treatment to be provided at the same institution
Key Exclusion Criteria	
 1. Benign biliary strictures 2. Malignancy secondary to Intraductal Papillary Mucinous Neoplasm 3. Surgically altered anatomy where ERCP is not possible 4. Previous biliary drainage using a SEMS or multiple plastic stents 5. Contraindications for endoscopic techniques 6. Patients who are currently enrolled in another investigational trial that would directly interfere with the current study 7. Pregnancy
Visits	
 • Screening • Baseline • Stent Placement Procedure Visit • Pre-Operative Follow-Up Visit (Week 1 and Monthly until Surgery or Transition to Palliation) • Biliary Reintervention Visit (as needed) • Curative Intent Surgery • Transition to Palliative Management Visit (as needed)

	
 • Post-Operative Follow-Up Visit (30 day Post-Surgery visit) • Long Term Follow-Up Visit (1 year after initial treatment for patients that have transitioned to palliation or 1 year post-stent placement for patients that have not undergone surgery or transitioned to palliation (with or without Neoadjuvant Therapy))
--	--

2 INTRODUCTION

This statistical plan addresses the planned analyses for the Preoperative Biliary SEMS RCT in Neoadjuvant Therapy based on the protocol dated 17 November 2014, Version AD. All of the specified analyses may not be provided in reports to Competent Authorities but may be used for scientific presentations and/or manuscripts.

3 ENDPOINT ANALYSIS

3.1 Primary Endpoint

Successful pre-operative biliary drainage defined as absence of reinterventions for the management of biliary obstructive symptoms.

- For patients undergoing surgery: from stent placement until surgery
- For patients transitioning to palliative management: from stent placement until transition to palliation

3.1.1 Hypotheses

Compared to the use of an Uncovered SEMS, use of a Fully Covered SEMS may present a higher risk of migration, but offers the ability to remove the stent were this deemed indicated by the treating endoscopist. Statistical testing will be performed to determine if the rate of success when using the Fully Covered SEMS is non-inferior to the rate of success when using the Uncovered SEMS. The following hypothesis will be tested:

$$H_0: \pi_{UC} - \pi_{FC} \geq \Delta \text{ (Inferior)}$$

$$H_a: \pi_{UC} - \pi_{FC} < \Delta \text{ (Non-inferior)}$$

where π_{FC} and π_{UC} are the probabilities of having success in the WallFlex Fully Covered Stent and WallFlex Uncovered Stent arms respectively, and Δ is defined as the non-inferiority margin.

3.1.2 Sample Size

The sample size was calculated for the test using an exact non-inferiority test in StatXact 9® software. The non-inferiority margin (Δ) is set at 20%. Each arm is assumed to have a success rate of 80.5%, which is the lower 95% CI boundary from the meta-analysis, which is done below. Given these assumptions a sample size of $51 \times 2 = 102$ patients provides 80% power to reject the null hypothesis listed above. If the p-value calculated for the test is below 0.05 it will be concluded that the test is significant and that the WallFlex Fully Covered stent is non-inferior to the WallFlex Uncovered stent.

In order to compensate for possible loss of patients to follow-up or per Endoscopist's decision to select the Uncovered stent based on ductal anatomy, namely stricture involving the lower cystic duct confluence, but randomized to Fully Covered, an additional 20% of patients will be enrolled giving a total sample size of 122 patients.

The success rate estimate is extracted from a full literature search which yielded nine articles (377 patients)^{2, 7, 21, 24, 25, 27, 29-31} on the use metal stents for pre-operative biliary drainage. The nine articles yielded a success rate estimate of 84.6% with a 95% CI of (80.5%, 87.9%).

3.1.3 Statistical Methods

The distribution of prognostic factors between patients with and without data will be examined on the primary endpoint. Statistical models that account for censored data may be employed in appropriate circumstances, e.g. for time-to-event outcomes. Sensitivity analyses will be conducted to assess the impact of missing data on the interpretation of the results, e.g. a tipping point analysis.

4 GENERAL STATISTICAL METHODS

4.1 Analysis Sets

Primary endpoint and selected secondary endpoints will be analyzed for the following cohorts.

Enrolled Cohort

A patient is considered “enrolled” after signing the study-specific ICF. Patients who sign the ICF but subsequently do not meet one or more of the eligibility criteria provided in Section 5.1 and Section 5.2 of the protocol will be considered screen failures and excluded from the study.

Intent-to-Treat Cohort (ITT)

This cohort consists of those “enrolled” subjects who meet all inclusion/exclusion criteria and are subsequently randomized.

Per-Protocol Cohort (PP)

The per-protocol cohort is a subset of the ITT patients who are treated per protocol and have no major protocol deviations (per ICH E9 definitions).

5 ADDITIONAL DATA ANALYSES

5.1 Secondary Endpoints

1. Occurrence and severity of adverse events related to the stent and/or stenting procedure
2. Occurrence and severity of surgical complications
3. Occurrence and severity of peri-surgical complications (up to 30 days after surgery)
4. Ability to deploy the stent in satisfactory position across the stricture (Stent Placement Success)
5. Improvement of biliary obstructive symptoms during stent indwell at Week 1 and Monthly until surgery or transition to palliation as applicable, compared to Baseline
6. Improvement of Laboratory Liver Function Tests (LFTs) until surgery for patients undergoing surgery, and at Week 1 and Monthly until transition to palliation, and at 1 year after stent placement for patients not undergoing surgery
7. Biliary Reintervention rate
8. Ability to complete neoadjuvant therapy as intended without stent related interruptions of neoadjuvant therapy
9. Stent migration rate
10. Assessment by surgeon of interference, if any, of SEMS on time to surgery and/or success of pancreaticoduodenectomy
11. For patients transitioning to palliative management: Successful biliary drainage defined as absence of reinterventions for the management of biliary obstructive symptoms from stent placement to 1 year after stent placement

5.2 Baseline Data

Patient demographics, clinical history, risk factors, obstructive symptoms, LFTs, tumor diagnosis, patient overall health, neoadjuvant therapy, and assessment of tumor invasion will be summarized using descriptive statistics (e.g., mean, standard deviation, n, minimum, maximum) for continuous variables and frequency tables for discrete variables.

5.3 Post-Procedure Endpoints

Post-procedure information will be collected at regularly scheduled follow-up examinations as detailed in the clinical study event schedule and will be summarized using descriptive statistics for continuous variables (e.g., mean, standard deviation, n, minimum, maximum) and frequency tables or proportions for discrete variables.

5.4 Subgroup Analyses

Stratified analyses will include tabulating the primary endpoint and select secondary endpoints by patients that undergo potentially curative surgery versus transition to palliation, by bilirubin level above or below 3 mg/dL, and gender.

5.5 Justification of Pooling

The analyses will be performed using data pooled across institutions. An assessment of the poolability of patients across sites and baseline characteristics will be made by fitting generalized linear models with site as the factor of interest and the primary endpoint as the outcome.

5.6 Multivariable Analysis

Univariate and multivariate analyses may be performed to assess the effect of potential predictors on the primary endpoint using logistic regression or Cox Proportional Hazards regression.

Variables from the following categories will be considered as possible predictors: demographics, tumor diagnosis, baseline LFTs, neoadjuvant therapy protocol, obstructive symptoms, baseline health status, and medical history. Factors from the univariate model will also be modeled multivariately using a stepwise procedure in a generalized linear model or Cox Proportional Hazards regression model. The significance thresholds for entry and exit into the model will be set to $p \leq 0.10$, with treatment assignment being manually kept in the model regardless of p-value.

5.7 Analysis of LFT's and Obstruction symptoms

For analysis of LFT's and obstruction symptoms, a paired t-test and McNemar's Test will be used to test differences from baseline. The data will also be analyzed using a generalized linear model, including treatment group and baseline covariates as predictors. Interactions between time and treatment group will be explored. Other possible predictors may include any but not limited to demographic/baseline data and medical history data. Different correlation structures will be fit to determine the best model fit.

5.8 Analysis of Impact of Adverse Events on Endpoints

For an analysis on the effect of the adverse events impact on time of surgery, length of hospitalization, and ICU stay, subjects with and without AEs will be analyzed to determine if any differences occur. Appropriate testing will be done to determine this, i.e. a 2x2 ANOVA analysis with a treatment by AE interaction.

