A literature review was conducted of clinical success of pre-operative biliary drainage using plastic or metal biliary stenting including all SEMS types used. Two associated meta-analyses were generated based on published reports of ratios of the number of patients experiencing clinical success in pre-operative biliary drainage without stent related complications over the total number of stented patients. A meta-analysis representing a total of 429 patients in six publications using plastic biliary stents yielded a biliary drainage success rate estimate of 45.9% [95% CI, 34.7% - 57.5%]. A meta-analysis representing a total of 377 patients in nine publications using SEMS yielded a biliary drainage success rate estimate of 84.6% [95% CI, 80.5% - 87.9%]. In patients who do ultimately undergo PD with curative intent, the SEMS is removed en-bloc inside the surgical specimen. Six of the 9 publications reporting on the use of pre-operative biliary drainage using SEMS state explicitly on the fact that SEMS do not interfere with successful PD and could be easily removed intra-operatively without complications. Some studies have reported an increased risk of post-operative wound infection, but there were no other reported increases in intra-operative or post-operative complications related to the use of SEMS. In addition, SEMS could be easily removed intra-operatively without complications.

Pre-operative biliary drainage (PBD) prior to Pancreaticoduodenectomy (PD) continues to be routine in many centers despite retrospective data showing that PBD increases post-operative wound infection. It was shown that these post-operative wound infections were classified on a grading scale of 1-5, with all reported occurrences rated as either 1 (oral medication and bedside intervention) or 2 (IV medication, TPN, enteral nutrition, or blood), and managed non-invasively. Other studies have also reported an increase in post-operative wound infection in the PBD group, but have indicated that although there is an increase in length of hospitalization, the length of time under anesthesia, amount of blood loss, and transfusion requirements were unaffected.

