#### **7.7. *Pre-Operative Follow-Up Visit – Phone and/or Office Visit***

- Week 1 and Monthly until surgery or transition to palliation as applicable
- Collection of Weight
- Patient's overall health status
- Assessment of Biliary Obstructive Symptoms
  - Right Upper Quadrant Pain
  - Fever/Chills
  - Jaundice
  - Itching
  - Dark urine
  - Pale stools
  - Nausea/Vomiting
- Laboratory Liver Function Tests (LFTs)
  - Serum Albumin level
  - Total Bilirubin
  - Alkaline Phosphatase
  - SGPT (ALT)

- Administered Neoadjuvant therapy
- Adverse events and reinterventions (as applicable)
- Device Events (as applicable)

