**Table 4: Adverse Event Definitions**

Term	Definition
	applicable, see MEDDEV 2.7/3 12/2010 for reporting timeline requirements.
Unanticipated Adverse Device Effect (UADE)  Ref: 21 CFR Part 812	Any serious adverse effect on health or safety or any life-threatening problem or death caused by, or associated with, a device, if that effect, problem, or death was not previously identified in nature, severity, or degree of incidence in the investigational plan or application (including a supplementary plan or application), or any other unanticipated serious problem associated with a device that relates to the rights, safety, or welfare of subjects.
Unanticipated Serious Adverse Device Effect (USADE)  Ref: ISO 14155-2011	Serious adverse device effect which by its nature, incidence, severity, or outcome has not been identified in the current version of the risk analysis report.  Note: Anticipated serious adverse device effect (ASADE) is an effect which by its nature, incidence, severity or outcome has been identified in the risk analysis report.
Device Deficiency  Ref: ISO 14155-2011  Ref: MEDDEV 2.7/3 12/2010	A device deficiency is any inadequacy of a medical device with respect to its identity, quality, durability, reliability, safety or performance.  Note: Device deficiencies include malfunctions, misuse or use errors, and inadequate labeling.  Note: All device deficiencies that could have led to a SADE if suitable action had not been taken or if circumstances had been less fortunate shall be reported as required by the local IRB/EC, national regulations, or the protocol. If applicable, see MEDDEV 2.7/3 12/2010 for reporting timeline requirements.

Abbreviations: EC=Ethics Committee; IRB=Institutional Review Board

Underlying diseases are not reported as AEs unless there is an increase in severity or frequency during the course of the investigation. Death should not be recorded as an AE, but should only be reflected as an outcome of a specific SAE (see **Table 4** for AE definitions).

All device-related events and all surgery related events experienced by the study patient after informed consent, whether during or subsequent to the procedure, must be recorded in the eCRF.

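### SAP 5.8 tests the effect of AEs on an undefined time of surgery by a 2x2 ANOVA with no AE-onset rule; if the outcome is the wait for surgery, a false delay can appear.

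*SAP*

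**What the plan says.** SAP 5.8 introduces the analysis with "For an analysis on the effect of the adverse events impact on time of surgery, length of hospitalization, and ICU stay". It then states that "subjects with and without AEs will be analyzed to determine if any differences occur", and gives the test as appropriate testing, "i.e. a 2x2 ANOVA analysis with a treatment by AE interaction". Time of surgery has no origin, unit or definition there, in the SAP's rules and definitions (7.3) or in the protocol. Neither document requires an AE to start before the outcome it is meant to affect.

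Four other places bear on the point:

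- **Nearest endpoint.** Secondary endpoint 10 (SAP 5.1) is "Assessment by surgeon of interference, if any, of SEMS on time to surgery and/or success of pancreaticoduodenectomy".
- **AE collection before surgery.** Pre-operative visits, at which AEs are recorded, run "Week 1 and Monthly until surgery or transition to palliation as applicable" (Protocol 7.7).
- **AE scope.** The text below Protocol Table 4 requires recording of "All device-related events and all surgery related events experienced by the study patient after informed consent". Protocol 7.13 follows operated patients for up to 30 days after surgery.
- **Censoring.** SAP 3.1.3, in the primary-endpoint section, says "Statistical models that account for censored data may be employed in appropriate circumstances". Protocol 8.4 makes the same statement as a commitment.

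**The concern.** If time of surgery is the wait from stent placement, a patient who waits six months has three times as long to acquire an AE as one who waits two. Grouping patients by whether they had an AE then partly sorts them by the outcome itself. The AE group waits longer on average even when AEs have no influence on scheduling. Patients who never reach surgery have no value to enter in the ANOVA and drop out of it. Surgery-related events, if counted, start at or after the outcome date.

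At stake is a statement that AEs delay surgery when the difference only reflects longer waits. SAP section 2 allows the specified analyses to be used in presentations and manuscripts, so such a statement could be published.

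**Working it through.** SAP 5.8 states no figure, so there is nothing of the plan's own to reproduce. The check sets out the two readings and then sizes the artefact under the first.

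**1. The two readings**

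- *Wait from stent placement to surgery.* The heading of 5.8 refers to endpoints, and endpoint 10 is the only listed endpoint on surgical timing. Protocol section 1 also gives avoiding delays to surgery as part of the rationale.
- *Operative duration.* The phrase stands beside hospital and ICU stay. Protocol section 1 discusses a similar group of measures, in which "the length of time under anesthesia, amount of blood loss, and transfusion requirements were unaffected". Hospital and ICU stay are not listed endpoints, so the heading does not decide the matter.

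**2. Inputs for the first reading**

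- Operated patients: Protocol section 1 reports that 25%-41% do not undergo the planned resection, so 122 x 0.59 = 72 to 122 x 0.75 = 92 (run as 70 and 90). It also cites 38% resected in borderline disease: 122 x 0.38 = 46.
- Wait T: uniform over 2-7 months. This is an assumption. The range is the protocol's for neoadjuvant chemoradiation, not for the wait, which also includes a resting and restaging period.
- Late AE hazard h: 3%-8% per month (assumption).
- Share q of patients with an AE on the day of placement: 0-20% (assumption; Protocol 9.1 lists both procedural and later effects).
- Share s with a surgical AE unrelated to the wait: 0, or 30%-50% (assumption).
- No true effect of AEs on the wait.

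**3. Formula**

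A patient waiting t months is AE-free with probability (1-q)(1-s)exp(-ht). Write M = [exp(-2h) - exp(-7h)]/(5h), so the probability of an AE is P = 1 - (1-q)(1-s)M. Let m0 be the mean wait of AE-free patients; q and s cancel from it. The overall mean is 4.5 = P·m1 + (1-P)·m0, so

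false delay = m1 - m0 = (4.5 - m0)/P.

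For h = 0.03, M = 0.8745 and m0 = 4.4375. For h = 0.08, M = 0.7023 and m0 = 4.3338. Example: q = s = 0, h = 0.03 gives 0.0625/0.1255 = 0.498 months, which at 30.4 days per month is 15.1 days.

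| q | s | P (h = 0.03 / 0.08) | False delay, days |
|---|---|---|---|
| 0 | 0 | 0.126 / 0.298 | 15.1 / 17.0 |
| 0.1 | 0 | 0.213 / 0.368 | 8.9 / 13.7 |
| 0.2 | 0 | 0.300 / 0.438 | 6.3 / 11.5 |
| 0 | 0.3 | 0.388 / 0.508 | 4.9 / 9.9 |
| 0 | 0.5 | 0.563 / 0.649 | 3.4 / 7.8 |

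If every AE occurs at placement (h = 0), m0 = 4.5 and the delay is zero.

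**4. False rejection**

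The AE effect adjusted for treatment was tested at the 5% level in simulated trials of 46 to 90 operated patients, with h from 0.03 to 0.08:

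- late AEs only: about 10%-39%;
- with placement-day AEs in 10%-20%: about 7%-30%;
- with surgical AEs in 30%-50%: about 5%-20%;
- all AEs at placement: about 5%.

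**5. Sensitivity to the spread of waits**

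These runs count pre-operative AEs only and include a lower setting (1% late hazard with 10%-20% placement-day AEs). Waits uniform over 3-6 months give 1-6 days and 5%-16% rejection. Gamma waits with mean 5 and SD 2.5 months give 8-44 days and 7%-72%. The assumed spread of waits matters as much as the AE hazard.

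**The case against.** The strongest reply is that the SAP writes time *to* surgery when it means delay (endpoint 10). Section 5.8 writes time *of* surgery, next to two peri-operative measures. Operative duration is then at least as plausible, and the waiting-time bias disappears. That stands, and it is why the point is conditional. It does not remove the gap: under that reading a post-operative AE could still be counted as affecting an operation already finished.

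Ever/never grouping is also an inference. The text speaks only of patients with and without AEs; ever/never is the natural reading of that in a 2x2 layout, but it is not written.

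It can further be said that the plan does not exclude surgical AEs, and that counting them dilutes the artefact. This is correct: the 15-17 day figure holds only if every counted AE arises late and before surgery.

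The censored-data clauses may cover patients without a surgery date. They do not settle when an AE must start, and 5.8 does not refer to them. Reading its i.e. as e.g. would leave the method open, but would define neither the outcome nor the onset rule.

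A reader might infer that the planned analysis is certain to report a false delay. The documents do not support that: they give no AE hazard, no placement-day share and no distribution of waits, and they leave the outcome itself open.

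**Conclusion.** The point holds as a conditional one. SAP 5.8 leaves the outcome undefined and sets no AE-onset rule. If the outcome is the wait for surgery, grouping patients by AE status can produce a false delay. Under the stated assumptions this is about 6-17 days with 7%-39% false rejection if only pre-operative AEs count, and about 3-10 days with 5%-20% if surgical AEs in 30%-50% of patients also count. It is nil if all AEs occur at placement. These figures are illustrative; the documents establish none of them. If the outcome is operative duration, the waiting-time bias is absent and only the onset gap remains.

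A reader might extend the bias to hospital stay, ICU stay or the interaction test. No bias is claimed for those, because the check above does not address them. Nor does the point reach the primary non-inferiority test or the sample size: this is an additional analysis with no success criterion. It is minor, and a cheap improvement.

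**What to change.** In SAP 5.8:

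1. Define time of surgery, with its start, end and unit.
2. Count only AEs related to the stent or stenting procedure with onset before the outcome: before surgery for the wait, before the start of the operation for operative duration.
3. If the outcome is the wait, replace the ANOVA by a Cox model with AE as a time-dependent covariate plus treatment, or by a landmark comparison among patients still awaiting surgery. Keep patients who do not reach surgery at risk until palliation, death or last follow-up. Report a cause-specific association, because palliation and death are competing events that may depend on AEs.

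In simulations with all 122 patients and no true effect, the time-dependent Cox test rejected in 4.3%-6.3% of trials and a 2-month landmark log-rank test in 4.3%-7.4%. That check assumed palliation independent of AEs, which is doubtful given the protocol's reasons for missed surgery (progression, comorbidity, declining performance status).

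The cost is a few sentences and modest programming. AE, surgery and palliation-visit dates are collected. A death date is not in the SAP 7.3 list of dates and should be confirmed as available. The main drawback is low precision. With no placement-day AEs, 1 - exp(-2h) = 5.8%-14.8% of patients have an AE by 2 months, or about 4-13 of 70-90 operated patients. A landmark also ignores AEs that start after it.
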